#### 8.1.2 Visit 1, Day 1, Enrollment (Vaccination), Clinic Visit

- Participant's willingness to participate will be reconfirmed and documented in the study records prior to performing any further study procedures, including administration of study vaccination.
- Eligibility criteria, including results from screening lab tests, will be reviewed with participants prior to the first study vaccination to ensure continued eligibility.
- Interim medical history, including an assessment for new medical conditions, stability of
  chronic diseases and symptoms suggestive of PIMMCs, will be obtained by interview of
  participants prior to study vaccination. Any changes in medical history since the
  screening visit will be reviewed with participants prior to study vaccination to ensure
  continued eligibility.
- All concomitant medications will be reviewed with participants prior to study vaccination for accuracy and completeness. Any new concomitant medications taken since the screening visit will be reviewed with participants prior to study vaccination to ensure continued eligibility. Medications reported in the eCRF are limited to those taken within 60 days prior to the first study vaccination.
- Vital signs (oral temperature, pulse, and BP) will be obtained prior to study vaccination to ensure continued eligibility. Vital signs assessed on Day 1 prior to study vaccination will be considered as baseline. Participants must not eat or drink anything hot or cold, or smoke within 10 minutes prior to taking oral temperature.

- A targeted physical examination, including an assessment for signs suggestive of PIMMCs, may be performed, by a study clinician licensed to make medical diagnoses and listed on the Form FDA 1572 as the site PI or sub-investigator, prior to study vaccination, if indicated based on review of complete medical history and any updates obtained by interview of participants since the screening visit. If not indicated, no physical examination is necessary.
- A urine pregnancy test will be performed locally by the site within 24 hours prior to study vaccination for all females of childbearing potential. Results must be negative and known prior to randomization and study vaccination. Women of childbearing potential will be counseled to avoid pregnancy until 60 days after the second (final) vaccination, i.e., Day 75.
- Venous blood will be collected prior to study vaccination for baseline serological assays (TNA and anti-PA ELISA).
- Participants will be randomized in Advantage eClinicalSM and randomly assigned to a treatment arm prior to study vaccination.
- Pre-administration reactogenicity assessments will be performed immediately prior to study vaccination to establish baseline.
- Participants will then receive one dose of study vaccine via a single IM injection into the
  deltoid muscle of the participant's preferred arm. The site of injection (right or left arm)
  and time of study vaccine administration will be recorded on the appropriate eCRF.
   Participants will be observed in the clinic for at least 30 minutes after study vaccination.
  The study vaccination site will be examined, post-administration reactogenicity
  assessments will be performed, and any AE/SAEs will be recorded on the appropriate
  eCRF prior to discharge from the clinic.
- Participants will be trained to complete a web based "eMemory Aid" and are expected to enter information in the eMemory Aid each day. Participants using the eMemory Aid will also be provided a paper memory aid for their use in the event they are unable to access the web-based system. The participants will be asked to enter the information from the paper memory aid into the eMemory Aid once they are able to access the web-based system. Participants will be provided with instructions on completion of the electronic memory aid and other study-related materials. They will learn to record daily oral temperature, solicited injection site and systemic reactions, unsolicited AEs, and concomitant medications. Participants will be encouraged to take their oral temperature around the same time each day. They must not eat or drink anything hot or cold, or smoke within 10 minutes prior to taking their oral temperature. Participants will be

instructed on how to use their memory aid and how to measure and record AEs prior to discharge from the clinic. They will be instructed to notify the study center if they develop any severe reactions after study vaccination. If the site PI or appropriate sub-investigator deems the reaction severe enough, further instructions will be given to the participant on the proper course of action, including a return to the clinic for immediate evaluation if appropriate.

## 8.2 Follow-up Visits

Follow-up visits are scheduled in reference to the study vaccination date as indicated for each visit window.

## 8.2.1 Visit 2, Day 8, Clinic Visit (End of Solicited Reactogenicity Period after First Vaccination)

(Window: Day 8 to Day 11, inclusive)

- Interim medical history, including an assessment for new medical conditions, stability of chronic diseases and symptoms suggestive of AESIs (PIMMCs), will be obtained by interview of participants and any changes since the previous clinic visit will be noted.
- All changes to concomitant medications will be recorded on the appropriate eCRF.
- All MAAEs and AE/SAEs will be recorded on the appropriate eCRF.
- eMemory Aid information will be reviewed with participants. If any reactogenicity events are on-going, they will be recorded as AEs.
- A targeted physical examination, including an assessment for signs suggestive of AESIs (PIMMCs), may be performed, if indicated based on review of interim medical history, by a study clinician licensed to make medical diagnoses and listed on the Form FDA 1572 as the site PI or sub-investigator.
- The study vaccination site will be examined.
- Venous blood will be collected for serological assays (TNA and anti-PA ELISA).
- Women of childbearing potential will be counseled to avoid pregnancy until 60 days after the second (final) vaccination, i.e., Day 75.

## 8.2.2 Visit 3, Day 15, Clinic Visit (Second Vaccination) (Window: Day 15 to 18, inclusive)

- Interim medical history, including an assessment for new medical conditions, stability of chronic diseases and symptoms suggestive of AESIs (PIMMCs), will be obtained by interview of participants and any changes since the previous clinic visit will be noted.
- All changes to concomitant medications will be recorded on the appropriate eCRF.
- All MAAEs and AE/SAEs will be recorded on the appropriate eCRF.
- A targeted physical examination, including an assessment for signs suggestive of AESIs (PIMMCs), may be performed, if indicated based on review of interim medical history, by a study clinician licensed to make medical diagnoses and listed on the Form FDA 1572 as the site PI or sub-investigator.
- Venous blood will be collected for serological assays (TNA and anti-PA ELISA).
- Criteria for receipt of the second vaccination will be reviewed with participants prior to
  the second study vaccination to ensure continued eligibility. These criteria are identical to
  the eligibility criteria, with the following exceptions: continued consent must be
  confirmed, age will not be re-confirmed, physical exam will not be required to determine
  good health, BMI will not be recalculated, screening labs will not be repeated, and
  screening electrocardiogram will not be repeated.
- Vital signs (oral temperature, pulse, and BP) will be obtained prior to study vaccination to ensure continued eligibility. Vital signs assessed on Day 1 prior to study vaccination will be considered as baseline. Participants must not eat or drink anything hot or cold, or smoke within 10 minutes prior to taking oral temperature.
- A urine pregnancy test will be performed locally by the site within 24 hours prior to study vaccination for all females of childbearing potential. Results must be negative and known prior to study vaccination. Women of childbearing potential will be counseled to avoid pregnancy until 60 days after the second (final) vaccination, i.e., Day 75.
- Pre-administration reactogenicity assessments will be performed immediately prior to study vaccination to establish baseline.
- Participants will then receive their second dose of study vaccine via a single IM injection into the deltoid muscle of the opposite arm of the first vaccination. The site of injection (right or left arm) and time of study vaccine administration will be recorded on the

appropriate eCRF. Participants will be observed in the clinic for at least 30 minutes after study vaccination. The study vaccination site will be examined, post-administration reactogenicity assessments will be performed, and any AE/SAEs will be recorded on the appropriate eCRF prior to discharge from the clinic.

- Participants will be re-trained to complete a web based eMemory Aid and are expected to enter information in the eMemory Aid each day. Participants using the eMemory Aid will also be provided a paper memory aid for their use in the event they are unable to access the web-based system. The participants will be asked to enter the information from the paper memory aid into the eMemory Aid once they are able to access the web-based system. Participants will be reminded to record daily oral temperature, solicited injection site and systemic reactions, unsolicited AEs, and concomitant medications. Participants will be encouraged to take their oral temperature around the same time each day. They must not eat or drink anything hot or cold, or smoke within 10 minutes prior to taking their oral temperature. Participants will be instructed on how to measure and record AEs prior to discharge from the clinic. They will be instructed to notify the study center if they develop any severe reactions after study vaccination. If the site PI or appropriate sub-investigator deems the reaction severe enough, further instructions will be given to the participant on the proper course of action, including a return to the clinic for immediate evaluation if appropriate.
- Note that all subsequent visits are based on the day that Visit 3 occurs. If it occurs on Day 15, all subsequent visits and windows are as written below. If it occurs after Day 15, subsequent visit days will be adjusted to maintain the intervals. For example, if Visit 3 occurs on Day 16, then the remaining target Days are 23, 30, 65, 196, and 381. The number of days in the accompanying acceptable windows for each visit will remain the same. The dates as written below reflect the schedule assuming that Visit 3 occurs on Day 15.

# 8.2.3 Visit 4, Day 22, Clinic Visit (End of Solicited Reactogenicity Period after Second Vaccination)

(Window: Day 22 to 25, inclusive)

- Interim medical history, including an assessment for new medical conditions, stability of chronic diseases and symptoms suggestive of AESIs (PIMMCs), will be obtained by interview of participants and any changes since the previous clinic visit will be noted.
- All changes to concomitant medications will be recorded on the appropriate eCRF.
- All MAAEs and AE/SAEs will be recorded on the appropriate eCRF.

- eMemory Aid information will be reviewed with participants. If any reactogenicity events are on-going, they will be recorded as AEs.
- A targeted physical examination, including an assessment for signs suggestive of AESIs (PIMMCs), may be performed, if indicated based on review of interim medical history, by a study clinician licensed to make medical diagnoses and listed on the Form FDA 1572 as the site PI or sub-investigator.
- The study vaccination site will be examined.
- Venous blood will be collected for serological assays (TNA and anti-PA ELISA).
- Women of childbearing potential will be counseled to avoid pregnancy until 60 days after the second (final) vaccination Day 75.

## 8.2.4 Visit 5, Day 29, Clinic Visit (Window: Day 27 to 31, inclusive)

- Interim medical history, including an assessment for new medical conditions, stability of chronic diseases and symptoms suggestive of AESIs (PIMMCs), will be obtained by interview of participants and any changes since the previous clinic visit will be noted.
- All changes to concomitant medications will be recorded on the appropriate eCRF.
- All MAAEs and AE/SAEs will be recorded on the appropriate eCRF.
- A targeted physical examination, including an assessment for signs suggestive of AESIs (PIMMCs), may be performed, if indicated based on review of interim medical history, by a study clinician licensed to make medical diagnoses and listed on the Form FDA 1572 as the site PI or sub-investigator.
- Venous blood will be collected for serological assays (TNA and anti-PA ELISA).
- Venous bloodwill be collected for standard clinical safety evaluations (tests outlined in Table 10).
- Women of childbearing potential will be counseled to avoid pregnancy until 60 days after the second (final) vaccination, i.e., Day 75.

## 8.2.5 Visit 6, Day 64, Clinic Visit (Window: Day 60-68, inclusive)

- Interim medical history, including an assessment for new medical conditions, stability of chronic diseases and symptoms suggestive of AESIs (PIMMCs), will be obtained by interview of participants and any changes since the previous clinic visit will be noted.
- All changes to concomitant medications will be recorded on the appropriate eCRF.
- All MAAEs and AE/SAEs will be recorded on the appropriate eCRF.
- A targeted physical examination, including an assessment for signs suggestive of AESIs (PIMMCs), may be performed, if indicated based on review of interim medical history, by a study clinician licensed to make medical diagnoses and listed on the Form FDA 1572 as the site PI or sub-investigator.
- Venous blood will be collected for serological assays (TNA and anti-PA ELISA).
- Women of childbearing potential will be counseled to avoid pregnancy until 60 days after the second (final) vaccination, i.e., Day 75.

## 8.2.6 Visit 7, Day 195, Clinic Visit (Window: Day 188 to 202, inclusive)

- Interim medical history, including an assessment for new medical conditions, stability of chronic diseases and symptoms suggestive of AESIs (PIMMCs), will be obtained by interview of participants and any changes since the previous clinic visit will be noted
- All changes to concomitant medications will be recorded on the appropriate eCRF only if they occurred after Day 64 and in relation to an MAAE, SAE, or AESI (PIMMC).
- MAAEs, SAEs, and AESIs (PIMMCs) will be recorded on the appropriate eCRF.
- A targeted physical examination, including an assessment for signs suggestive of AESIs (PIMMCs), may be performed, if indicated based on review of interim medical history, by a study clinician licensed to make medical diagnoses and listed on the Form FDA 1572 as the site PI or sub-investigator.
- Venous blood will be collected for serological assays (TNA and anti-PA ELISA).

## 8.3 Final Visit

## 8.3.1 Visit 8, Day 380, Clinic Visit (Window: Day 373 to 387, inclusive)

- Interim medical history, including an assessment for new medical conditions, stability of chronic diseases and symptoms suggestive of AESIs (PIMMCs) will be obtained by interview of participants and any changes since the previous clinic visit will be noted.
- All changes to concomitant medications will be recorded on the appropriate eCRF only if they occurred after Day 64 and in relation to an MAAE, SAE, or AESI (PIMMC).
- MAAEs, SAEs, and AESIs (PIMMCs) will be recorded on the appropriate eCRF.
- A targeted physical examination, including an assessment for signs suggestive of AESIs (PIMMCs) may be performed, if indicated based on review of interim medical history, by a study clinician licensed to make medical diagnoses and listed on the Form FDA 1572 as the site PI or sub-investigator.
- Venous blood will be collected for serological assays (TNA and anti-PA ELISA).

## **8.4** Early Termination Visit (if needed)

The following activities will be performed at the Early Termination Visit on participants who withdraw, or are withdrawn or terminated from this trial:

- Interim medical history, including an assessment for new medical conditions, stability of chronic diseases and symptoms suggestive of AESIs (PIMMCs), will be obtained by interview of participants and any changes since the previous clinic visit will be noted.
- All changes to concomitant medications will be recorded on the appropriate eCRF if within the window.
- All MAAEs and AE/SAEs will be recorded on the appropriate eCRF, if within the windows.
- eMemory Aid information will be reviewed with participants, if not previously completed and reviewed.

- Vital signs (oral temperature, pulse, and BP) may be obtained if indicated. Participants must not eat or drink anything hot or cold, or smoke within 10 minutes prior to taking oral temperature.
- A targeted physical examination, including an assessment for signs suggestive of AESIs (PIMMCs) may be performed, if indicated based on review of interim medical history, by a study clinician licensed to make medical diagnoses and listed on the Form FDA 1572 as the site PI or sub-investigator.
- The study vaccination site will be examined, if the early termination falls from Days 1 to 8 after either study vaccination.
- Post-administration reactogenicity assessment will be performed, if the early termination falls from Days 1 to 8 after either study vaccination.
- Venous blood will be collected for clinical safety labs and auto-antibodies, if not previously drawn.
- Venous blood will be collected for serological assay (TNA and anti-PA ELISA).

## 8.5 Unscheduled Visit (if needed)

An Unscheduled Visit may occur at any time during this trial. Any of the following activities may be performed:

- Interim medical history, including an assessment for new medical conditions, stability of chronic diseases and symptoms suggestive of AESIs (PIMMCs) will be obtained by interview of participants and any changes since the previous clinic visit or phone call will be noted (if indicated).
- All changes to concomitant medications will be recorded on the appropriate eCRF, if within the window.
- All MAAEs and AE/SAEs will be recorded on the appropriate eCRF, if within the windows.
- eMemory Aid information will be reviewed with participants, if applicable.
- Vital signs (oral temperature, pulse, and BP) may be obtained if indicated. Participants must not eat or drink anything hot or cold, or smoke within 10 minutes prior to taking oral temperature.

- A targeted physical examination, including an assessment for signs suggestive of AESIs (PIMMCs), may be performed, if indicated based on review of interim medical history, by a study clinician licensed to make medical diagnoses and listed on the Form FDA 1572 as the site PI or sub-investigator.
- The study vaccination site will be examined, if the unscheduled visit falls from Days 1 to 8 after either study vaccination.
- Post-administration reactogenicity assessment will be performed, if the unscheduled visit falls from Days 1 to 8 after either study vaccination.
- Venous blood will be collected for clinical safety labs and serological testing (TNA and anti-PA ELISA), if not already performed.

## 9 ASSESSMENT OF SAFETY

## 9.1 Specification of Safety Parameters

Safety will be assessed by the frequency and severity of the following:

- 1. SAEs occurring from the time of the first study vaccination through approximately 12 months after the second study vaccination (approximately Day 380).
- 2. Solicited AEs reactogenicity events occurring from the time of each study vaccination (Day 1) through Day 8 after each study vaccination (or until resolved):
  - a) Injection site reactions including pruritus, ecchymosis, erythema, edema/induration, pain, and tenderness.
  - b) Systemic reactions including fever, feverishness, fatigue, malaise, myalgia, arthralgia, headache, and nausea.
- 3. Clinical safety laboratory AEs occurring from the time of the first study vaccination through approximately Day 29. Parameters are found in Table 10.
- 4. Unsolicited AEs –non-serious unsolicited AEs occurring from the time of the first study vaccination through approximately Day 64.
- 5. AESIs (PIMMCs) and MAAEs occurring from the time of the first study vaccination through approximately Day 380.

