**Table 1: Study Objectives and Outcome Measures** 

Primary Objective: Safety	Primary Safety Outcome Measures

 
To assess the safety of lyophilized and liquid formulations of AV7909.
 
	Occurrence of all SAEs through approximately 12 months following receipt of the second study vaccination (approximately Day 380).
	
 
Occurrence of abnormal clinical safety laboratory AEs at approximately Day 29.
 

	Occurrence of all protocol specified AESIs (i.e., PIMMCs) and MAAEs, from the time of the first study vaccination through approximately 12 months following the second vaccination (approximately Day 380).
	Occurrence of unsolicited non-serious adverse events from the time of the first study vaccination through approximately Day 64.
Primary Objective: Tolerability	Primary Tolerability Outcome Measures
To assess the tolerability of lyophilized and liquid formulations of AV7909.	Occurrence of solicited injection site and systemic reactogenicity events in the week after each study vaccination (Days 1 through 8 and Days 15 through 22, inclusive).
Secondary Objective: Immunogenicity	Secondary Immunogenicity Outcome Measures
To obtain initial estimate of comparative immunogenicity of liquid and lyophilized formulations of AV7909.	• Geometric mean titer and 95% confidence intervals of antibodies assayed by toxin neutralization assay (ED 50 and NF 50 ) and anti-PA IgG by ELISA in each study group before vaccination and on approximately Days 8, 15, 22, 29, 64, 195, and 380.
	• Proportion and 95% confidence intervals of participants in each study group with seroconversion for antibodies detected by TNA and ELISA (defined as a ≥4-fold increase over baseline levels, or a ≥4-fold increase over the lower limit of quantification [LLOQ] if the baseline value is < LLOQ) on approximately Days 8, 15, 22, 29, 64, 195, and 380.
	• Proportion and 95% confidence intervals of participants in each study group with putative seroprotection (defined as NF 50 ≥ 0.56) before vaccination and on approximately Days 8, 15, 22, 29, 64, 195, and 380.
Exploratory Immunogenicity Objectives	Exploratory Immunogenicity Study Outcomes
Exploratory Immunogenicity Objectives	

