Vaccine Administration Risks. The risk profile for AVA (BioThrax) is well known, given that millions of persons have been vaccinated. The risks of AV7909 are less well characterized, given that fewer persons have been vaccinated with this product.

Risks of AVA (BioThrax). Since the licensure of BioThrax in 1970, more than 3.3 million individuals, primarily military personnel, have been vaccinated in the pre-exposure setting. The safety profile of BioThrax and its associated risks are summarized in the BioThrax prescribing information. The most common ( $\geq 10\%$ ) local (injection-site) adverse reactions observed in clinical studies are tenderness, pain, erythema, edema, and arm motion limitation. The most common ( $\geq 5\%$ ) systemic adverse reactions are muscle aches, headache, and fatigue.

Risks of CPG 7909. CPG 7909 has been investigated clinically since the mid-1990s for indications that have included cancer monotherapy, combination use with anti-cancer therapies, and vaccine adjuvant against infectious diseases and cancers. Potential risks associated with AV7909 include hypersensitivity reactions, autoimmune reactions, and more minor local and systemic reactogenicity effects. Other oligonucleotides have been evaluated as vaccine adjuvants, including CPG1018, the adjuvant in Heplisav-B, a hepatitis B vaccine now licensed in the US for persons 18 years and older.

Risks of AV7909. Emergent BioSolutions has sponsored three completed clinical studies in healthy participants 18 through 50 years of age as part of the AV7909 development program: a phase 1, a phase 1/2, and a phase 2 trial.  A total of 241 participants have been exposed to a

combination of AVA and CPG7909. In the initial trial, a formulation with AVA + 1.0 mg CPG 7909 was tested and was well tolerated with a trend toward increased frequency and severity of local and systemic reactions in the AV7909 formulation compared to BioThrax. The second trial identified a formulation of AV7909 with a lower CPG7909 concentration (0.25 mg CPG 7909) for further clinical development that produced an enhanced immune response without increased reactogenicity. This formulation was evaluated in the phase 2 trial described below and is the formulation to be tested in the current study.

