Because of this potential risk, individuals with a history of autoimmune disorders or active autoimmune disease (PIMMCs) will be ineligible for this trial. Additionally, because of the possibility of a delay between the vaccination and onset of symptoms indicative of a disease process of this kind, all participants will be followed for PIMMCs throughout the trial (for 12 months after the second vaccination, to approximately Day 380). PIMMCs will be captured as "Adverse Events of Special Interest" (AESI). Blood samples will be collected before vaccination from all participants for possible laboratory evaluation should suspicion of a PIMMC arise during study participation. Participants who discontinue study treatment will be encouraged to attend all subsequent clinic visits and safety follow-up contacts to facilitate this monitoring.

Local Reactogenicity. During clinical testing in which 241 participants were exposed to the combination of BioThrax + CPG 7909, the most common local reactions were mild to moderate pain, tenderness, and arm motion limitation. These reactions often resolved within 48 hours after vaccination. The most common local AEs (reported in ≥ 5% of participants in at least one of the AV7909 arm(s) from the three completed clinical trials) included injection site pain, arm movement impairment, warmth, edema/induration, erythema, hemorrhage, and pruritus.

Systemic Reactogenicity. During clinical testing to date, in completed trials in which participants were exposed to the combination of BioThrax + CPG 7909, systemic reactogenicity manifested primarily as mild to moderate fatigue, muscle ache, and headache. The most common systemic AEs (reported in  $\geq$  5% of participants in at least one of the AV7909 arm(s) from the three completed clinical trials) included fatigue, myalgia, headache, respiratory rate increased, pyrexia, pharyngolaryngeal pain, nausea, upper respiratory tract infection, and chills.

Laboratory Findings. During clinical testing to date, in completed trials in which participants were exposed to the combination of BioThrax + CPG 7909, the most common reported laboratory findings after vaccination were hypokalemia, lymphocyte count decreased, leukopenia, hypoglycemia, blood creatine phosphokinase increased, and hemoglobin decreased.

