## 9.2.2 Reactogenicity

Reactogenicity events are solicited AEs that are common and known to occur following administration of this type of study vaccine. The following Toxicity Grading Scales will be used to grade solicited injection site and systemic (subjective and quantitative) reactions:

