#### 9.3.1. Solicited Events and Symptoms

Systemic solicited adverse events were collected pre-vaccination, and systemic and local solicited adverse events were collected 30 minutes post-vaccination and then daily for 7 days after each vaccination and graded on a scale of 0 (absent), 1 (mild), 2 (moderate) and 3 (severe). Systemic events include fever, feverishness, fatigue, malaise, myalgia, arthralgia, headache, and nausea, with grading scales as defined in Table 8; the quantitative grading scale for fever is included in Table 9. Injection site events include pain, tenderness, pruritus, ecchymosis, erythema/redness, and edema/induration with grading scales as defined in Table 6. Ecchymosis, erythema/redness, and edema/induration are measured by both functional and measurement grading scales as defined in Table 7.

The number and percentage of subjects reporting at least one solicited adverse event will be summarized for each solicited adverse event, any systemic symptom, any local symptom, and any symptoms. Corresponding 95% CIs will be calculated using Clopper-Pearson methodology from a binomial distribution (SAS Proc Freq with a binomial option). Solicited events occurring post first vaccination will be presented in Table 35, post second vaccination in Table 36, and post any vaccination in Table 37. Summaries of solicited events following any vaccination will be stratified by sex in Table 38 and stratified by age category in Table 39.

For each systemic and local event, any systemic event, any local event, and any solicited event, the maximum severity over 7 days after each vaccination will be summarized for the safety population. The number and percentage of subjects reporting each event will be summarized by the maximum severity and study arm, separately for each vaccination and over all vaccinations (Table 40, Table 41 and Table 42).

The number of subjects reporting a solicited adverse event will be summarized for each day post vaccination for each vaccination and for all vaccinations combined both in tabular form (Table 43, Table 44, Table 45 and Table 46) and graphically in bar charts (Figure 15 and Figure 16). A comparison of the event rate for each study arm between vaccination 1 and vaccination 2 will be presented in Table 47.

Solicited adverse events by subject will be presented in Listing 10 and Listing 11.

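### Arm motion limitation, one of the three most common local reactions the protocol reports for this vaccine, is not a solicited term, so it falls outside the primary tolerability outcome and is collected only as an unsolicited event.

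*Protocol*

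**What the plan says.** The primary tolerability outcome in protocol Table 1 is "Occurrence of solicited injection site and systemic reactogenicity events in the week after each study vaccination". Protocol section 9.1 gives the local part of that list: "Injection site reactions including pruritus, ecchymosis, erythema, edema/induration, pain, and tenderness". Section 7.1 and the grading scale in Table 5 carry the same six terms. On the SAP side, section 9.3.1 states "Injection site events include pain, tenderness, pruritus, ecchymosis, erythema/redness, and edema/induration", and section 4.5.2, Table 6 and the shells for Tables 35 to 46 agree.

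Protocol section 9.2.2 describes the class: "Reactogenicity events are solicited AEs that are common and known to occur following administration of this type of study vaccine".

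Protocol section 2.3.1 reports what is known about local reactions in three places:

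- For BioThrax plus CPG 7909 (241 participants): "the most common local reactions were mild to moderate pain, tenderness, and arm motion limitation".
- For local events in at least 5% of at least one AV7909 arm: "injection site pain, arm movement impairment, warmth, edema/induration, erythema, hemorrhage, and pruritus".
- For AVA, at 10% or more: "adverse reactions observed in clinical studies are tenderness, pain, erythema, edema, and arm motion limitation".

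**The concern.** A reaction that the protocol itself puts among the commonest has no solicited item, no grading scale and no row in the solicited-event tables. Tolerability is a primary objective, and its single outcome is built from solicited events. For each solicited symptom, protocol section 11.6.2 and SAP section 9.3.1 promise a proportion with an exact interval and a maximum severity after each dose. The SAP adds a day-by-day profile, and the protocol allows a test between arms. None of that will exist for arm motion limitation as a solicited symptom.

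The trial sets two formulations of one vaccine side by side. A local effect that is already known and frequent is where a difference in tolerability could show. If it is left to unsolicited reporting, its rate is likely to be too low, and what is reported will be counted under a separate primary outcome, unsolicited events through Day 64.

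**Working it through.** **1. Known local reactions against the solicited list.** Arm movement impairment is treated here as the same reaction as arm motion limitation (an assumption about wording).

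| Reaction | Most common, BioThrax + CPG 7909 | At least 5% in an AV7909 arm | At least 10%, AVA | Solicited here |
|---|---|---|---|---|
| Pain | yes | yes | yes | yes |
| Tenderness | yes | no | yes | yes |
| Arm motion limitation | yes | yes | yes | **no** |
| Erythema | no | yes | yes | yes |
| Edema/induration | no | yes | yes | yes |
| Pruritus | no | yes | no | yes |
| Ecchymosis (nearest listed term: hemorrhage) | no | yes | no | yes |
| Warmth | no | yes | no | **no** |

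Two reactions appear in all three lists: pain and arm motion limitation. The first is solicited and the second is not.

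**2. Whether another item captures it.** Grades for pain and tenderness rise with interference with daily activity, but they start from awareness of pain and do not record arm movement. Myalgia and arthralgia are footnoted in protocol Table 7 as excluding the injection site. The remaining route is an unsolicited event. Under protocol section 9.2.1 that yields a description, onset and resolution dates, severity and relatedness, but no prompted daily grade.

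**3. What a solicited item would deliver at 20 per arm.** The plan's own precision figures come first. Clopper-Pearson limits are the 2.5% quantile of Beta(x, n−x+1) and the 97.5% quantile of Beta(x+1, n−x).

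- 10/20 gives 27.2% to 72.8%, and 20/40 gives 33.8% to 66.2%. Both match protocol Table 12 (27-73 and 34-66).
- The chance of at least one case is 1 − (1−p)^n. At p = 10% this is 1 − 0.9^20 = 87.8% and 1 − 0.9^40 = 98.5%. Protocol Table 11 prints 87 and 98.

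The documents give no rate for arm motion limitation, so the following use an assumed range:

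- Chance of at least one case in an arm: 64% at a 5% rate, 88% at 10%, 98.8% at 20%.
- Exact 95% intervals: 1/20, 0.1% to 24.9%; 2/20, 1.2% to 31.7%; 6/20, 11.9% to 54.3%.
- Smallest contrast detectable with 80% power (Fisher's exact test, two-sided 0.05): about 10% against 53%, 20% against 68%, 30% against 78%, or 50% against 92%.

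**4. What unsolicited reporting delivers.** If a fraction s of true cases is reported, the observed rate is p × s. With the same s in both arms, a difference d shrinks to d × s. The documents give no value for s, so this is illustration only. Take true rates of 50% and 80%:

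| Assumed s | Observed rates | Fisher power, 20 per arm |
|---|---|---|
| 1 | 50% and 80% | 41% |
| 0.5 | 25% and 40% | 11% |
| 0.25 | 12.5% and 20% | 5% |

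The table shows the direction of the effect. It is not an estimate for this trial.

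**The case against.** The strongest reply is that the reaction is collected and will be analysed. Participants are trained to enter unsolicited events in the daily aid (protocol 8.1.2 and 8.2.2). They are asked about them when diary entries are confirmed at Days 8 and 22 (Appendix A, note 13), and the vaccination site is examined after each dose and at those visits. SAP Table 48 then gives a count, percentage and exact interval by preferred term and arm, and Tables 49 and 50 add severity and relatedness. All of this stands. A reader might infer that the arms cannot be compared on arm motion limitation at all, or that a participant has nowhere to record it. The documents support neither. What is lost is quality of ascertainment: the prompts do not name the term.

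Other parts of the reply, and what remains of each:

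- Section 9.2.2 describes what solicited events are and does not undertake to solicit every common one. This stands. The omission is a design choice that needs a reason, not a breach of a stated rule.
- The word including in section 9.1 could leave the list open. This does not stand: the grading scale in protocol Table 5 and the SAP shells close it at six terms.
- The eMemory Aid itself is not in the documents. True, so its lack of an item is inferred from those lists.
- A reader might infer that rarer terms such as ecchymosis were preferred. That is unsupported: no ecchymosis rate is given, and section 2.3.1 lists hemorrhage at the same 5% threshold as arm movement impairment.
- Limitation may seldom occur without pain or tenderness, so the any-symptom row might hardly change. The documents cannot settle this. The term's own rate and severity are missing either way.
- The study is descriptive, between-arm tests are optional, and 20 per arm detects only very large contrasts. True. The gain is mainly a better estimate, not a powered test.

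**Conclusion.** The point holds as a gap in the primary tolerability outcome. Of the three local reactions named as most common, two are solicited and arm motion limitation is not. It therefore has no solicited proportion, interval, daily profile or maximum severity, and it cannot enter the any-injection-site-symptom row. An arm-level estimate remains available through SAP Table 48, by weaker ascertainment and under a different outcome.

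The size cannot be stated. The sources are thresholds: at least 5% in at least one AV7909 arm, and at least 10% for AVA alone. In an arm of 20 these correspond to 20 × 0.05 = 1 and 20 × 0.10 = 2 participants. The 241 earlier participants also included some given a 1.0 mg CPG 7909 formulation rather than the 0.25 mg one tested here. A reader might want to turn this into a number of missed cases, but that needs a reporting fraction for which the documents give no basis. That the rate will be understated is a judgement about unsolicited against solicited collection, not a figure in the plan.

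**What to change.** Add arm motion limitation to the solicited injection-site list in protocol 7.1, 9.1 and Table 5, to the eMemory Aid, and to SAP 4.5.2, 9.3.1, Table 6 and the solicited-event tables from Table 35 on. Warmth is optional. Grade it on the functional scale that Table 5 already uses for ecchymosis, erythema and edema. If the omission was deliberate, state the reason.

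A new solicited local term would also come under the Grade 3 diary alert (protocol section 12) and the individual and study halting criteria that refer to solicited events (9.5.1 and 9.5.2). Those passages must be reconciled with the changed list. How the term counts there is for the sponsor to settle.

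The SAP refers to data already collected under protocol Version 3.0, so some or all participants may already be dosed. For them, show unsolicited reports of the term within 7 days of each dose in a separate, labelled row by arm. SAP Listing 12 already carries days since the associated dose. Fix the qualifying preferred terms before unblinding, do not pool this row with solicited rates, and state the limitation in the CSR. If the diary changes during the trial, show results before and after the change separately.

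The cost is one more diary item and its table rows, a diary-version change that mixes two methods of ascertainment, and possibly a higher rate of any local symptom. The sample size does not change.
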